15.1 EXTENT OF EXPOSURE

Duration of exposure, actual cumulative dose, average daily dose, dose intensity (DI) and relative dose intensity (RDI) will be summarized descriptively by the dose. Counts and percentages of subjects who have dose reductions, interruptions and dose escalation will be summarized by dose. In addition, counts and percentage of subjects who received the assigned dose will be presented. The calculations will be performed to include both the mean and median for the parameters and their respective interquartile ranges.

[REDACTED]
[REDACTED]
[REDACTED]

Cumulative Dose:

Cumulative dose of a study treatment is defined as the total dose (mg) given during the study treatment exposure. The planned cumulative dose for a study treatment refers to the total planned dose as per the protocol up to the last date of study treatment administration. The actual cumulative dose refers to the total actual dose administered, over the duration for which the subject is on the study treatment as document in the DAR eCRF. It is the sum of the non-zero total daily doses recorded over the dosing period.

[REDACTED]
[REDACTED]
[REDACTED]

[REDACTED]	[REDACTED] [REDACTED]
------------	--------------------------

15.2 ADVERSE EVENTS

Adverse events will be collected and recorded from the time a subject sign the informed consent to the end of study period. All AEs will be classified by primary system organ class (SOC) and preferred term (PT) according to MedDRA coding dictionary. A treatment-emergent adverse event (TEAE) is an AE that begins after the first administration of Vodobatinib or any existing AEs that worsens after then first dose of Vodobatinib. All reported AEs will be listed, but only TEAEs will be summarized in tables. The reporting period for TEAE begins from the date of first dose of Vodobatinib until 30 days after the last dose of Vodobatinib. Any AE which occurs 30 days after the last dose will be reported if it is considered related to Vodobatinib by the investigator.

An overall summary of TEAEs presenting number and percentage of subjects reporting at least one TEAE for the categories presented below:

- Subjects with at least one TEAE
- Subjects with at least one TEAE related to Vodobatinib
- Subjects with at least one serious TEAE
- Subjects with at least one serious TEAE related to Vodobatinib
- Subjects with at least one TEAE leading to premature discontinuation of Vodobatinib
- Subjects with at least one TEAE leading to death
- TEAEs by highest relationship to Vodobatinib
- TEAEs by highest severity

The following summaries will be tabulated

- TEAEs overall and by SOC and PT
- Study Vodobatinib-related TEAEs, overall and by SOC and PT
- TEAEs by maximum severity, overall and by SOC and PT
- Study Vodobatinib-related TEAEs by maximum severity, overall and by SOC and PT
- Serious TEAEs, overall and by SOC and PT
- Vodobatinib-related Serious TEAEs, overall and by SOC and PT
- CTCAE grade 3 or higher TEAEs
- Vodobatinib-related CTCAE grade 3 or higher TEAEs
- TEAEs leading to discontinuation of Vodobatinib, overall and by SOC and PT

- Vodobatinib related TEAEs leading to discontinuation of Vodobatinib, overall and by SOC and PT
- TEAEs leading to death, overall and by SOC and PT
- Vodobatinib related TEAEs leading to death, overall and by SOC and PT
- TEAE leading to dose interruption/adjustment, overall and by SOC and PT
- Vodobatinib related TEAEs leading to dose interruption/adjustment, overall and by SOC and PT
- Dose Limiting Toxicities
- Summary of CVAEs
 - Subjects with at least one CVAE
 - Subjects with at least one CVAE related to Vodobatinib
 - Subjects with at least one grade 3 or higher TEAEs
 - Subjects with at least one grade 3 or higher TEAEs related to Vodobatinib
 - Subjects with at least one serious CVAE
 - Subjects with at least one serious CVAE related to Vodobatinib
 - Subjects with at least one CVAE leading to premature discontinuation of Vodobatinib
 - Subjects with at least one CVAE related to Vodobatinib leading to premature discontinuation of Vodobatinib
 - Subjects with at least one CVAE leading to death
 - Subjects with at least one CVAE leading to death due to Vodobatinib
- CVAEs by PT all Grades and Grade 3 or higher
- CVAEs related to Vodobatinib by PT all Grades and Grade 3 or higher

For summaries by SOC and PT, a subject will be counted only once at the SOC level and once at each PT within the SOC level, even if the subject experienced more than one AE within a specific SOC and PT. For summaries by SOC, PT, and maximum severity, a subject will be counted only once at the maximum severity level for which the event occurred at the SOC level and at the maximum severity level for which the event occurred for each unique PT within that SOC level. Therefore, subjects will contribute to only one severity level within a PT or SOC.

Summaries presenting frequency of TEAEs by SOC and PT will be ordered by overall descending frequency of SOC and then, within a SOC, by overall descending frequency of PT. Summaries presenting TEAEs by PT only will be ordered by overall descending frequency of PT.

Subject listings of all adverse events will be provided. Deaths and other serious or clinically significant non-fatal adverse events will be listed separately.

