Eligible subjects will be treated in [REDACTED] cycles with once-daily, oral self-administered 174 mg of K0706 and will be evaluated for K0706 anti-leukemic activity (hematological, cytogenetic and molecular response). Intra patient dose escalation is permitted only for Part C subjects enrolled at [REDACTED]. Patients enrolled in Part C at [REDACTED] can be escalated upto 174 mg based on investigator's assessment of subject's tolerability and response.

Adverse events (AEs) will be assessed throughout the study until 30 days after discontinuation of the study drug. AEs will be graded as per National Cancer Institute, Common Terminology Criteria for Adverse Events (NCI-CTCAE) Version 5.0. Any AE/SAE reported by the patient after the completion of AE collection period and considered related to the study drug should also be reported by the investigator. AEs will be followed to a satisfactory resolution, until it becomes stable, or until it can be

explained by another known cause (i.e. concurrent condition or medication) and the clinical judgment of Investigator indicates that further evaluation is not warranted. Disease progression is not considered an AE in this study unless it leads to death or hospitalization in which case it should be reported as SAE.

A Data Safety Monitoring Board (DSMB) will be established for periodic review of safety data for this study.

The study will consist of screening wherein all the required clinical and laboratory investigations to establish the eligibility of the subject for the trial is completed. Subject's disease diagnosis and status will be confirmed using the pathology reports available with the subject at the time of screening initiation. Only the latest pathology reports, subsequent to which there has been no change in therapy (with a potential to affect the disease course), will be considered for screening. Pathology reports and documented intolerance on the prior TKIs received by the subject will be reviewed for eligibility assessment.

The screening must be performed unless extension of screening period is granted by the CRO/sponsor medical monitor after an evaluation of the impact of the extended period on assessment of efficacy and safety.

Subjects will enter the study center on Day 1 to receive the first administration of IMP and will complete the required assessments and sample collections.

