15 SAFETY ANALYSIS STRATEGY

All analyses described in this section will be performed on the Safety Analysis set and will be presented by dose. The results will be descriptive in nature. All data will be summarized and listed.

Safety will be assessed based on exposure, adverse events (AEs/SAEs), laboratory assessments (hematology, chemistry and urinalysis), vital signs, 12-Lead electrocardiograms (ECGs) and physical examination.

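### In the readable SAP, exposure and CVAEs are tabulated by dose, with CVAEs only as crude subject counts or percentages; the three Part C disease cohorts share one dose, so no planned summary shows either by cohort

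*SAP*

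**What the plan says.** **Grouping.** SAP 15 sets the rule for all safety output: "All analyses described in this section will be performed on the Safety Analysis set and will be presented by dose". SAP 15.1 repeats it for exposure: "Duration of exposure, actual cumulative dose, average daily dose, dose intensity (DI) and relative dose intensity (RDI) will be summarized descriptively by the dose". That section adds means, medians and interquartile ranges.

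**Measure.** SAP 15.2 opens with "An overall summary of TEAEs presenting number and percentage of subjects reporting at least one TEAE for the categories presented below". The CVAE block starts with "Subjects with at least one CVAE" and continues in the same form for related, serious, fatal and discontinuation events, followed by CVAEs by preferred term and grade. Under SAP 6.1 the percentage denominator is the number of subjects in the analysis set unless stated otherwise.

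**Window.** "The reporting period for TEAE begins from the date of first dose of Vodobatinib until 30 days after the last dose of Vodobatinib". After that, "Any AE which occurs 30 days after the last dose will be reported if it is considered related to Vodobatinib by the investigator".

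**Listings.** SAP 15 says that all data will be listed as well as summarised, and 15.2 adds "Subject listings of all adverse events will be provided".

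**Part C.** Subjects take "once-daily, oral self-administered 174 mg of K0706" (Protocol 3). Those enrolled in Part C at another, redacted, dose are outside the Part C statistical analysis (SAP 3.2). Protocol 3 and 7.3.1 treat the three disease cohorts as distinct populations to be evaluated separately for efficacy and safety. Protocol 7.8.3.2 repeats this, and 7.8.9 plans AE summaries by dose and by disease cohort.

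**The concern.** The protocol asks for safety cohort by cohort, while the readable SAP tabulates by dose. With one analysed dose in Part C, the SAP grouping cannot separate chronic, accelerated and blast phase. SAP 8 asks for disease type in the baseline tables; the readable text of SAP 15 does not.

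The second part is the measure. Subjects stay on drug until progression, intolerance or withdrawal, for about 60 months and possibly longer (SAP 3.2). A blast-phase subject can meet the progression rule over 4 weeks (Protocol 7.3.2.3). A percentage of subjects with at least one event rises with time on drug even when the risk per year is the same.

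What is at stake is the reading of long-term CVAE data. I take CVAE to mean cardiovascular adverse event; the readable text does not spell it out. The SAP gives these events their own tables. Every Part C subject has had ponatinib, and Protocol 7.1.1 names vascular occlusion with that drug.

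**Working it through.** The plan states no figure to reproduce. The check is a comparison of texts, then an illustration in which every rate and duration is assumed.

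**1. Texts side by side**

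| Item | Protocol, Part C | SAP, readable text |
|---|---|---|
| Safety grouping | Cohorts A, B, C separately (3, 7.3.1, 7.8.3.2) | By dose (15) |
| AE tables | Dose and disease cohort (7.8.9) | By dose (15, 15.2) |
| Exposure | No cohort summary named | By dose (15.1) |
| CVAE measure | None named | Subjects with an event, over subjects (15.2, 6.1) |
| Person-time or rate for AEs | None | None |

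The time-to-event sentences in Protocol 3, Protocol 7.8 and SAP 6.1 name no adverse event.

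**2. How a crude percentage depends on time on drug**

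Assume a constant hazard h per year, the same in every cohort, and a fixed time on drug t. Add the 30-day tail d = 30/365.25 = 0.082 y.

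Crude proportion = 1 − exp(−h(t + d)).

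With h = 0.10 and t = 24, 12 and 4 months (labelled CP, AP, BP):
- CP: 1 − exp(−0.10 × 2.082) = 18.8%
- AP: 1 − exp(−0.10 × 1.082) = 10.3%
- BP: 1 − exp(−0.10 × 0.415) = 4.1%

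Other assumed inputs:

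| Hazard per 100 patient-years | Months on drug | Crude % |
|---|---|---|
| 5 | 24 / 12 / 4 | 9.9 / 5.3 / 2.1 |
| 20 | 24 / 12 / 4 | 34.1 / 19.5 / 8.0 |
| 10 | 36 / 9 / 3 | 26.5 / 8.0 / 3.3 |
| 10 | 18 / 6 / 2 | 14.6 / 5.7 / 2.5 |
| 10 | 12 / 12 / 12 | 10.3 / 10.3 / 10.3 |

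The spread within each row reflects the assumed exposure and nothing else. The last row shows that equal exposure produces no distortion.

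**3. What the added figures would do**

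*First-event rate.* Mean time at risk to first event or end of window is (1 − exp(−h(t + d)))/h. For CP this is 0.188/0.10 = 1.88 y, so the rate is 0.188/1.88 = 0.10. For BP it is 0.0407/0.407 = 0.10. Under a constant hazard the rate returns 10 per 100 patient-years in both.

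*Exposure columns alone.* Dividing a crude proportion by the group's own mean exposure gives a rough rate. With h = 0.05: 0.0287/0.5 = 5.7 per 100 at 0.5 y, and 0.1428/3 = 4.8 per 100 at 3 y, against a true 5. Over h from 0.03 to 0.08 and mean times of 0.5 and 3 y, the extremes are:
- +15%: h = 0.03, fixed 0.5 y, 0.0173/0.5 = 0.0346
- −17%: h = 0.08, exponential time with mean 3 y, [1 − exp(−0.08 × 0.082)/(1 + 0.24)]/3 = 0.199/3 = 0.0663

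**4. Precision**

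Exact Poisson 95% limits for k events in P patient-years are χ²(0.025; 2k)/(2P) and χ²(0.975; 2k + 2)/(2P).
- 5 events in 100 patient-years: 5.0 per 100 (1.6 to 11.7)
- 2 events in 30 patient-years: 6.7 per 100 (0.8 to 24.1)

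**The case against.** **Person-time can be derived.** A reader might infer that no CVAE rate by cohort can be obtained. The documents do not support that: SAP 15 promises listings of all safety data and counts exposure among them, so cohort person-time can be worked out. This stands. The gap is a planned summary, not the data.

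**Cohort presentation can be inferred.** The protocol evaluates each cohort separately for safety, and SAP 15 counts exposure as safety. Taken together, exposure by cohort is a fair reading. Taken alone, the SAP groups events and exposure consistently, both by dose. So it would be too strong to say that the SAP abandons the protocol's intention. Still, neither document specifies exposure by cohort, and programmers will follow the SAP's explicit by-dose rule.

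**Redaction.** Blocks are blacked out in SAP 6.1 and directly after the exposure paragraph in 15.1. Relevant text may sit there, so the point is confined to readable text.

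**No comparison is planned.** Protocol 7.3.1 says the cohorts can be regarded as three separate studies. A reader might infer that a planned cross-cohort CVAE comparison is biased; none is planned. What remains is that even one cohort's percentage is hard to interpret without its time at risk.

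**Little precision.** Cohort sizes are redacted, and step 4 shows how wide an interval from few events can be. This argues for keeping the rate as a supplement.

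**Conclusion.** The point holds as a cheap, low-priority improvement. In the readable text, the SAP's by-dose rule merges Cohorts A, B and C at 174 mg although the protocol wants their safety evaluated separately, and CVAEs appear only as crude counts or percentages despite treatment times that can range from weeks to 60 months or more.

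The size of any distortion is unknown. The percentages in the working rest on an assumed constant and equal hazard and on assumed times on drug, and they vanish as a contrast when exposure is equal. They do not show that any cohort's CVAE risk would be misreported by a given amount. The tables are descriptive, the MTD/RP2D rests on DLTs, and no planned decision changes.

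**What to change.** Keep the crude tables and add the following.

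1. **SAP 15.1:** show Part C exposure (total patient-years, mean, median) by Cohort A, B and C, for subjects in the Part C analysis.
2. **SAP 15.2:** show the CVAE tables by Cohort A, B and C as well.
3. **SAP 15.2:** add subjects with a first CVAE per 100 patient-years, with an exact Poisson 95% CI. Time runs from first dose to the first event or, if none, to the earliest of last dose + 30 days, death or data cut-off. Count only events inside that window and list later related events separately. Use the same CVAE definition as the crude table.

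The minimum is item 1 placed beside item 2, which already allows a rough rate.

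**Cost:** SAP wording, three more columns in the exposure and CVAE tables, and one rate table. It uses AE onset and dosing dates already collected, so no new data are needed. The downsides are wide intervals in small cohorts and a constant-hazard assumption, so the rate supplements the crude percentage and does not replace it.

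### Two of the ten rows in the SAP's cardiovascular AE summary are specified for TEAEs instead of CVAEs

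*SAP*

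**What the plan says.** SAP section 15.2 defines the term first: "A treatment-emergent adverse event (TEAE) is an AE that begins after the first administration of Vodobatinib", extended to existing events that worsen after the first dose. Nothing in the definition refers to an organ system.

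The section then lists the AE tabulations. Among the general ones are "CTCAE grade 3 or higher TEAEs" and "Vodobatinib-related CTCAE grade 3 or higher TEAEs", together with maximum-severity tables for all TEAEs and for related TEAEs. Further down comes "Summary of CVAEs", with ten sub-rows. Its third and fourth sub-rows are "Subjects with at least one grade 3 or higher TEAEs" and "Subjects with at least one grade 3 or higher TEAEs related to Vodobatinib". The row before them is "Subjects with at least one CVAE related to Vodobatinib" and the row after them is "Subjects with at least one serious CVAE".

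Two further bullets plan CVAEs by preferred term, for all grades and for Grade 3 or higher: one for all CVAEs and one for those related to the drug.

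**The concern.** A subject-level summary of one event class should have every row drawn from that class, so that each row is a subset of the first. Here the two severity rows name a wider class. Read against the SAP's own definition, they take in every severe treatment-emergent event, including the cytopenias that would be expected in a leukemia trial.

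What is at stake is one clear safety figure: how many subjects had a severe cardiovascular event, overall and related to the drug. The documents show an interest in it. Protocol section 7.1.1 lists cardiac arrhythmias and heart failure among the AEs reported with this class of drug and notes vascular occlusion with ponatinib. Part C requires prior ponatinib (Protocol 7.3.2.1.1, criterion 3), SAP section 8 summarises baseline cardiovascular co-morbidities, and section 15.2 gives CVAEs their own table.

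**Working it through.** There is no plan figure to reproduce. The check compares row labels with definitions.

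**Step 1. Event type named in each row of the CVAE summary (SAP 15.2).**

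| Row | Content (paraphrased) | Event type named |
|---|---|---|
| 1 | Any event | CVAE |
| 2 | Related | CVAE |
| 3 | Grade 3 or higher | **TEAE** |
| 4 | Grade 3 or higher, related | **TEAE** |
| 5 | Serious | CVAE |
| 6 | Serious, related | CVAE |
| 7 | Led to stopping the drug | CVAE |
| 8 | Related, led to stopping the drug | CVAE |
| 9 | Led to death | CVAE |
| 10 | Led to death, attributed to the drug | CVAE |

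Eight of ten rows name CVAE and two name TEAE (8 + 2 = 10). The text of both rows is legible and the same word appears in each, so this is not a redaction or a broken line.

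**Step 2. What the literal wording counts.** Let A be the subjects with at least one CVAE, B those with at least one Grade 3 or higher CVAE, and G those with at least one Grade 3 or higher TEAE. I take CVAEs in the tables to be treatment-emergent, since section 15.2 tabulates only TEAEs.

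- B is contained in A, so a correctly restricted row 3 can never exceed row 1: |B| ≤ |A|.
- B is also contained in G, so the literal row 3 can only match or exceed the intended one: |G| ≥ |B|.
- Nothing ties G to A. |G| > |A| is possible, which would put a severity row above the any-event row of the same table.

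The same argument applies to row 4 against row 2, with the related versions of each set.

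**Step 3. Whether the literal rows add anything.** G and its related counterpart are the populations of "CTCAE grade 3 or higher TEAEs" and "Vodobatinib-related CTCAE grade 3 or higher TEAEs". The maximum-severity tables, planned overall as well as by SOC and PT, cover the same ground. The literal rows would therefore repeat general counts inside a cardiovascular table.

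**Step 4. Whether |B| is available elsewhere.** The only other severe-CVAE outputs are the two by-PT bullets. Many of the general tables are specified overall and by SOC and PT; these two bullets do not say overall. The section's counting rule counts a subject once at each PT. Applying that rule here, with n_k the number of subjects with Grade 3 or higher CVAE term k:

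max(n_k) ≤ |B| ≤ Σ n_k

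The upper limit is reached only if no subject has two different severe CVAE terms. The by-PT counts bound the figure but do not give it. As specified, no table reports |B|, overall or related.

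**Step 5. If the restriction is inferred from the heading.** Rows 3 and 4 would then hold |B| and its related counterpart, which is the intended content. The printed labels would still say TEAEs and would misdescribe the counts.

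**The case against.** The strongest reply is that the rows sit under a cardiovascular heading, and the heading sets their scope. The general severe-TEAE tables are already listed, so the literal reading makes the rows redundant. Since only treatment-emergent events are tabulated at all, the author may have used TEAE loosely for a treatment-emergent event within this table. The by-PT bullets point the same way: the intended severity split was of CVAEs. This part stands. The wording looks like a drafting slip, and a sensible programmer may well read it as intended.

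It does not remove the point. TEAE is defined a few lines earlier in the same section, and a specification should not depend on a programmer departing from a defined term. On the inferred reading, the label is still wrong.

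A second reply is that a literally programmed row would match its own label, so the fault would be a missing row and not a false figure. That is fair as far as it goes, though a reader of a cardiovascular table would naturally take its rows as cardiovascular. It is also true that every AE is to be listed by subject, so the count could be recovered, and that the unseen table shell for the by-PT output might carry a total line. Neither is a specified summary of the figure.

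A third reply concerns importance. A reader might infer that the protocol names cardiovascular and vascular toxicity as the class concern. It does not. Protocol 7.1.1 places arrhythmias and heart failure in a list with fluid retention, myelosuppression, hepatotoxicity and others, and mentions vascular occlusion separately, as specific to ponatinib.

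**Conclusion.** The inconsistency is certain: two of ten rows use the wrong event type, judged by the SAP's own definition and by the other eight rows. The consequence is conditional. If the rows are programmed literally, the general severe-event counts appear in the cardiovascular table, a subset row can exceed its parent, and the subject-level severe-CVAE count is missing. If the restriction is inferred, only the labels are wrong.

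A reader might infer that the table will report the overall severe-toxicity rate as cardiovascular. The documents support this only as a risk of the wording. A reader might also want a factor by which severe cardiovascular events would be overstated. None can be given: no rate of severe TEAEs or of severe CVAEs is readable in either document.

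The effect stays within one table. SAP section 15 describes the safety results as descriptive, Protocol 7.8 plans no formal testing, and no endpoint, sample size or stopping rule in the readable text uses these rows. It should be corrected, but it does not threaten the trial's conclusions on efficacy. The readable SAP does not show how a CVAE is identified; parts of it are redacted, so that is not counted here.

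**What to change.** In SAP section 15.2, under the CVAE summary, replace the word TEAEs with CVAE in the third and fourth sub-rows. They would then count subjects with at least one Grade 3 or higher CVAE, and subjects with at least one Grade 3 or higher CVAE related to Vodobatinib. Make the same change in the table shell and its programming specification.

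The cost is two words in the SAP and the matching shell text. It needs no new data and changes nothing in the design or in any other analysis. The general Grade 3 or higher TEAE tables stay as they are.
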